6.3 Recruitment

Sample

The study will recruit 40 participants for consultations in the development of the intervention (focus groups and individual interviews, for further details see **Stage 2a: Work Package 2**), and a total of 60 people with dementia and their carers in the feasibility RCT. People with dementia will be recruited from Memory Clinics and Community Mental Health Teams (CMHTs). The control condition will be usual care, and use of drugs will be documented for both conditions. Recruitment will take place in two NHS Trusts, the Camden and Islington Foundation Trust (C&IFT), and the Barnet, Enfield and Haringey Mental Health Trust. We predict that a minimum of one dyad per week will be recruited into the study. This is based on previous experience from the REMCARE trial, during which the lead Applicant recruited an average of 8 people with dementia per month in London, and the recently completed iCST trial which recruited on average 9 people per month.

Recruitment Strategy

People with dementia living in the community and their carers will be recruited from a variety of settings including CMHTs, memory clinics, outpatient clinics, and day centres. Essential baseline

information will be recorded at registration, with people with dementia individually randomised using an adaptive scheme. People on cholinestarease inhibitors or antidepressant medication will continue taking them. The researcher and the PI will make close links with the local memory clinic and community mental health teams through regular attendance and contact.

Participant recruitment at a site will only commence when the trial has:

1. Been confirmed by the Sponsor (or it's delegated representative), and
2. Been issued an 'NHS permission letter'.

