11.3 Sample size calculation

Proposed sample size for feasibility trial

No formal power calculations are undertaken in feasibility studies, instead sufficient participants are recruited in order to determine factors such as attrition and recruitment rates and how these are related to feasibility for a full scale RCT. A total of 60 people will be recruited (56,57), which will allow calculation of 95% Confidence Intervals (CI) in the acceptable ranges for continuation to the main trial with the minimum size needed to estimate acceptability being 56 expected value 75% (95% CI = 59-87%). We will recruit to the study over 15 months, with an average of 4 dyads recruited per month.

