11.4 Planned recruitment rate

People with dementia will be recruited from Memory Clinics and Community Mental Health Teams (CMHTs). Recruitment will take place in two NHS Trusts, the Camden and Islington Foundation Trust (C&IFT), and the Barnet, Enfield and Haringey Mental Health Trust. We predict that a minimum of one dyad per week will be recruited into the study, based on previous experience from the REMCARE trial, and the recently completed iCST trial. The recruitment period is 17 months inclusive of the

development phase of the intervention and feasibility trial. The start date for the feasibility RCT is August 2017. Full details of timeline appear in Appendix 2.

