Appendix 1 - Flow diagram of recruitment and follow-up of participants

IDEA Project timetable and milestones

February 2016	Start of the IDEA Project
February 2016 – July 2016	Ethics Approval
May 2016 – October 2016	Appointment of Research Assistant
February 2016 – September 2016	Systematic review of Behavioural Activation interventions for older people – Work Package 1
August 2016 – October 2016	First draft of the IDEA Intervention Manual – Work Package 1
November 2016 – January 2018	Recruitment for Work Package 2 & 3
November 2016 - February 2017	Consultations with users, carers and dementia care professionals about the IDEA Intervention Manual – Work Package 2
February 2017	Consultation with Experts/ Experts Workshop about the IDEA Intervention Manual - Work Package 2
March 2017	Analyses of Qualitative data - Work Package 2
March 2017	Second draft of the IDEA Intervention Manual - Work Package 2
February 2017 – April 2017	Development of all Intervention Materials
April 2017 – May 2017	Field-testing of the Intervention
May 2017 – July 2017	Intervention Refinement – Final draft of the IDEA Intervention Manual
August 2017 – January 2017	Feasibility RCT
October 2017 – March 2018	Follow-up assessments at 4 months
February 2018 – July 2018	Follow-up assessments at 8 months
July 2018 – October 2018	Analyses of feasibility data
May 2018- October 2018	Publication of qualitative findings
February 2019 – July 2019	Publication of feasibility RCT findings
November 2019	Dissemination event
August 2019- January 2020	Grant Application for main Trial

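### The protocol's recruitment rate and timetable do not deliver 60 dyads: Appendix 2 appears to give the RCT about six months, which at 4 dyads per month is about 24

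*Protocol*

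**What the plan says.** **Size.** Section 6.3 plans "a total of 60 people with dementia and their carers in the feasibility RCT". Sections 8.2 and 11.3 justify the number by precision: at least 56 are needed to estimate acceptability, with an expected value of 75% and a 95% interval of 59–87%.

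**Rate and duration.** Section 11.3 continues: "We will recruit to the study over 15 months, with an average of 4 dyads recruited per month". Section 6.3 says "We predict that a minimum of one dyad per week will be recruited into the study", and Section 11.4 repeats this. Section 6.3 supports it with average rates of 8 and 9 people per month in two earlier trials. Section 11.4 says "The recruitment period is 17 months inclusive of the" development phase and the feasibility trial together, then "The start date for the feasibility RCT is August 2017", and refers to Appendix 2 for the timeline.

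**Timetable (Appendix 2).**
- Recruitment for Work Packages 2 and 3: "November 2016 – January 2018".
- Final draft of the manual: May to July 2017.
- Feasibility RCT: "August 2017 – January 2017".
- 4-month follow-up: "October 2017 – March 2018".
- 8-month follow-up: February to July 2018.
- Analysis of feasibility data: July to October 2018.

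**Total duration.** Sections 2 and 8.7 give 20 months overall and 8 months per participant; Section 8.7 counts the 20 months from recruitment of the first participant.

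**The concern.** The 15 months in Section 11.3 match one row of Appendix 2 exactly, but that row also serves the consultations and the field-testing. It opens nine months before the RCT does. RCT recruitment cannot sensibly start earlier, because Section 7.1 says the RCT tests the manual that comes out of field-testing. A rate that yields 60 over 15 months therefore seems to have been paired with a randomisation period of about six.

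Two things are at stake. First, 60 was chosen so that acceptability, the primary feasibility outcome in Section 11.1, could be estimated with a stated precision; a much smaller trial would not give it. Second, the number of dyads recruited per month is itself a feasibility outcome (Sections 8.4 and 11.2) meant to inform the main trial. It will be harder to interpret if the protocol implies more than one planned rate.

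**Working it through.** **1. The plan's own figure.** Dyads = months × rate = 15 × 4 = 60. This reproduces.

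**2. Where 15 months occurs.** November 2016 to January 2018, counted inclusively, is 15 calendar months. November 2016 to July 2017 is 9 of them, all before the August 2017 start. 15 − 9 = 6.

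**3. The RCT window.** The printed end, January 2017, precedes the start. I read it as January 2018, because the recruitment row ends then and both follow-up rows are six months long. August 2017 to January 2018 is 6 calendar months, 184 days, 184/7 = 26.3 weeks.

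**4. Yield over that window.**

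| Rate | Source | Dyads | Share of 60 |
|---|---|---|---|
| 4 per month | Section 11.3 | 6 × 4 = 24 | 40% |
| 1 per week (minimum) | Sections 6.3, 11.4 | about 26 | 43% |
| 8 per month | Section 6.3, earlier trial | 6 × 8 = 48 | 80% |
| 9 per month | Section 6.3, earlier trial | 6 × 9 = 54 | 90% |

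None reaches 60 or 56. The rate needed is 60/6 = 10 per month, 2.5 times the stated average.

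**5. Precision.** Acceptability of the intervention can be observed only in those who receive it. Assuming 1:1 allocation (the protocol gives no ratio), 24 to 26 dyads put 12 or 13 in the intervention arm. Exact (Clopper–Pearson) 95% intervals near 75%:
- 9/12 (75%): 43–95%
- 10/13 (77%): 46–95%

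The protocol states 59–87%. For comparison on the same basis, 30 in the arm gives 54–88% (22/30) or 58–90% (23/30).

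**6. Follow-up rows.** Questionnaires fall 4 and 8 months after randomisation. Randomisation from August 2017 to January 2018 implies:

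| Visit | Implied | Appendix 2 |
|---|---|---|
| 4 months | December 2017 – May 2018 | October 2017 – March 2018 |
| 8 months | April – September 2018 | February – July 2018 |

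The 4-week visit window shown in Appendix 4 does not close the gap. A participant randomised on 1 August 2017 could be seen no earlier than 3 November 2017. For 8-month visits to end in July 2018, randomisation must stop in November 2017 (4 months × 4 = 16 dyads) or, using the window, December 2017 (5 × 4 = 20).

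**7. Total duration.** If the 15 months were RCT-only, recruitment would run from August 2017 to October 2018, past the last listed follow-up. It would also need 15 + 8 = 23 months, against the stated 20. Working back from 20, 20 − 8 = 12 months × 4 = 48 dyads, still below 56.

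**The case against.** **The sample size is not built on 15 × 4.** Correct. A reader might infer that 60 was derived from that product, but Section 11.3 rests it on precision and adds the rate afterwards as a recruitment plan. The problem is deliverability, not the derivation.

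**One per week is a minimum.** Also correct. A reader might infer that the trial cannot reach 60; the documents do not support that. Twenty-six is a floor, and the past rates would bring 80–90% of target. What stands is that no rate in the protocol reaches 60, or even 56, in six months.

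**Six months is an inference.** The printed date is impossible, the row is labelled as the RCT rather than its recruitment, and the follow-up rows do not fit a January 2018 end. This is fair, so the reading is given as an assumption. The follow-up rows do not rescue the plan: the 8-month row implies an earlier stop to randomisation and fewer dyads.

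**Section 11.3 may mean the whole project.** Its reference to the study could cover development and RCT together, which would explain the match with the 15-month row. But then 4 per month over 15 months must also supply the consultations and the 15 field-test dyads, and does not give 60 to the RCT.

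**The 17 months is not a rival RCT window.** Agreed: Section 11.4 says it includes development. It still disagrees with the combined 15-month row in the appendix to which that section refers.

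**The outcome is descriptive.** A reader might infer that 4 per month counts as success under Section 11.3 and failure under Appendix 2. The protocol sets no recruitment threshold, so that goes too far; the observed rate can be reported whatever was planned.

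**Conclusion.** The point holds as an internal contradiction in the recruitment plan. At the stated average of 4 per month, the apparent RCT window yields about 24 of 60 dyads. At the stated minimum of one per week it yields about 26, and at the cited past rates 48 to 54. All fall short of 60 and of the protocol's own minimum of 56. The follow-up rows and the 20-month duration are out of step with the same plan.

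The six-month window rests on reading the RCT row as ending in January 2018. The arm-level interval of roughly 43–95% rests on 1:1 allocation as well, and on recruitment at 4 per month or one per week.

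This is a planning defect in a descriptive feasibility study. It biases no estimate and is no error in a power calculation, but the stated size and precision do not follow from the stated rate and dates.

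**What to change.** State one recruitment window for the RCT alone, with its matching monthly rate, separate from development-phase recruitment. Carry it through Sections 11.3 and 11.4, Appendix 2 (the RCT row with a corrected end date, both follow-up rows and the analysis row), and the total duration in Sections 2 and 8.7. State in Section 11.4 what the combined period covers, and make it agree with Appendix 2.

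Then choose one of two courses:
- **Keep 60**, and set window, rate and duration so that they deliver it. At 4 per month this means 15 months of RCT recruitment and 23 months from first randomisation to last follow-up, so the 20-month figure must change too. A shorter window needs a higher rate, up to 10 per month for six months, with a reason to expect it.
- **Keep the timetable**, and restate the expected number of dyads and the interval for acceptability that it supports.

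The cost is wording and a revised timetable, plus a longer calendar if 60 is kept at 4 per month.

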11.4 Planned recruitment rate

People with dementia will be recruited from Memory Clinics and Community Mental Health Teams (CMHTs). Recruitment will take place in two NHS Trusts, the Camden and Islington Foundation Trust (C&IFT), and the Barnet, Enfield and Haringey Mental Health Trust. We predict that a minimum of one dyad per week will be recruited into the study, based on previous experience from the REMCARE trial, and the recently completed iCST trial. The recruitment period is 17 months inclusive of the

development phase of the intervention and feasibility trial. The start date for the feasibility RCT is August 2017. Full details of timeline appear in Appendix 2.

11.5 Randomisation methods

The Sealed Envelope service will provide the randomisation and feasibility data that will be useful to collect in order to inform the main trial. The main purpose of randomisation is to test its feasibility and acceptability for people with dementia and their carers. Random allocation lists will be generated by Sealed Envelope.

11.6 Statistical analysis

11.6.1 Summary of baseline data and flow of participants

Essential baseline information will be recorded which will include quantitative and qualitative information. This will include specifics of diagnosis of dementia, psychiatric illness, and use of medications such as cholinestarease inhibitors or antidepressants. Details of demographic data will also be recorded such as gender, education, living status, and ethnicity. The feasibility trial will also produce a consort flow diagram in order to inform the main trial.

11.6.2 Primary outcome analysis

In line with current recommendations of GCP in the analysis of feasibility studies, analyses will be descriptive. We will conduct descriptive statistics for rates of recruitment, follow-up, attrition and adherence. We will calculate adherence to treatment by calculating the percentage in the Behavioural Activation group completing all sessions. Baseline characteristics of the sample will be presented using means and SDs or 95 CI% (as well as medians, IQR or percentages). We will also calculate descriptive statistics for outcome measures, at baseline, 4 months, and 8 months, and changes in scores from baseline (means, SDs, IQRs), in order to derive estimates for the fully powered RCT. All analyses will be undertaken using SPSS.

11.6.3 Secondary outcome analysis

Several clinical outcome measures will be evaluated for suitability for the main trial. Depressive symptoms are proposed as the outcome for the future fully powered study. For further details of all proposed clinical outcome measures for the full trial see section 8.4.

11.6.4 Sensitivity and other planned analyses

Missing data and non-compliance to the intervention will be measured as primary outcomes for this feasibility trial. A more detailed statistical analysis plan will be produced as a separate document by the Project Statistician. Formal records will be kept of the statistical analysis plan and how it can inform the main RCT.

12 Record keeping and archiving

At the end of the trial, all essential documentation will be archived securely by the PI for a minimum of 20 years from the declaration of end of trial. Essential documents are those which enable both the conduct of the trial and the quality of the data produced to be evaluated and show whether each site complied with all applicable regulatory requirements. The sponsor will notify the coordinating site (where all data will be stored) when trial documentation can be archived. All archived documents will continue to be available for inspection by appropriate authorities upon request.

13 Oversight Committees

Trial Steering Committee

A Trial Steering Committee (TSC) has been set-up and will include an independent Chair and two independent members, along with the study's CI, and other study collaborators. The Committee will meet once a year. The TSC will be combined with the Independent Data Monitoring Committee, given that this is a small feasibility RCT study. The TSC will discuss issues related to data collection, ethical issues and other incidents.

Research governance and conduct of the trial

The trial will be conducted in line with the Helsinki Declaration. University College London is the nominated sponsor.

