11.1 Primary Outcome

Feasibility primary outcome

- The acceptability of the intervention for people with dementia and their carers which will be measured by the number of those finding the intervention acceptable

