11.2 Secondary outcome(s)

- Willingness of clinicians to recruit and people with dementia to be randomised (number of dyads recruited per month and any barriers or facilitators to recruitment)
- Number of eligible participants that consent to the study
- Follow-up rates and number completing each outcome measure proposed for the main trial
- Number of sessions attended
- Standard deviations of outcome measures to estimate the sample size in a fully powered RCT

Proposed clinical outcome measures

- These will be evaluated for suitability for the main trial. Depressive symptoms is proposed as the outcome for the future fully powered study. Carers will complete generic health and quality of life measures (EQ-5D, SF-12), and resource use questionnaires to examine feasibility of cost-effectiveness analysis. Questionnaires will be completed at baseline, 4 and 8-months after randomisation. For further details see Section 8.4.

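### The protocol names two conflicting sets of primary outcomes, and its primary outcome analysis section omits acceptability, the outcome that sizes the trial

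*Protocol*

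**What the plan says.** Section 11.1 gives a single entry under its primary heading: "The acceptability of the intervention for people with dementia and their carers which will be measured by the number of those finding the intervention acceptable". Section 11.3 ties its minimum size of 56 to estimating that quantity, with an expected value of 75% and a 95% interval of 59% to 87%. It says that the total of 60 permits confidence intervals "in the acceptable ranges for continuation to the main trial". Section 8.2 repeats this justification.

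Section 11.2 lists as secondary, among others, "Follow-up rates and number completing each outcome measure proposed for the main trial" and "Number of sessions attended".

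Section 11.6.2 is headed Primary outcome analysis. It says "We will conduct descriptive statistics for rates of recruitment, follow-up, attrition and adherence" and, on adherence, "We will calculate adherence to treatment by calculating the percentage in the Behavioural Activation group completing all sessions". It goes on to baseline characteristics and to clinical scores at baseline, 4 and 8 months. Acceptability is not mentioned there, nor in 11.6.3 or 11.6.4. The only 95% interval in section 11.6 belongs to baseline characteristics.

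Section 11.6.4 says: "Missing data and non-compliance to the intervention will be measured as primary outcomes for this feasibility trial". Its next sentence promises a more detailed, separate statistical analysis plan.

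**The concern.** Missing data is the complement of follow-up and completion of measures. Non-compliance is the complement of sessions attended. The same quantities are thus secondary in 11.2 and primary in 11.6.4, while the outcome that 11.1 calls primary is absent from the section meant to analyse it.

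The trial exists to inform a decision about a fully powered trial. If acceptability were poor and completeness good, or the reverse, the protocol would support calling either one the primary result. That should be fixed before any result is seen. The analysis section should also contain the one interval that the trial was sized to produce.

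**Working it through.** **Labels side by side.**

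| Quantity | 11.1 | 11.2 | 11.3 | 11.6.2 | 11.6.4 |
|---|---|---|---|---|---|
| Acceptability | primary | not listed | basis of the minimum of 56 | absent | absent |
| Follow-up and completion (missing data) | not listed | secondary | attrition named as a general aim only | described | primary |
| Sessions attended, adherence (non-compliance) | not listed | secondary | not mentioned | described | primary |

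No section reconciles the second and third rows with the first. This contradiction rests on text and needs no arithmetic.

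**The plan's own figure.** Inputs from 11.3: n = 56, expected proportion p = 0.75, stated 95% interval 59% to 87%.

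- Wald: p ± 1.96 × √(p(1 − p)/n) = 0.75 ± 1.96 × √(0.1875/56) = 0.75 ± 0.113, that is 63.7% to 86.3%.
- Wilson, 42/56: 62.3% to 84.5%.
- Exact (Clopper-Pearson), 42/56: 61.6% to 85.6%.
- Agresti-Coull, Jeffreys and Wilson with continuity correction give 62.2% to 84.6%, 62.6% to 84.9% and 61.4% to 85.2%.

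None of these is 59% to 87%. That interval fits a smaller sample, for example 30/40 by the exact method (58.8% to 87.3%).

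**Effect of the denominator.** Section 11.1 does not say who is counted. The control arm receives usual care only, so probably only Behavioural Activation participants can rate the intervention. The allocation ratio is not stated. Assuming 1:1, 60/2 = 30 people with dementia could do so.

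| Raters | Wald | Wilson | Exact |
|---|---|---|---|
| 60 | 64.0% to 86.0% | 62.8% to 84.2% | 62.1% to 85.3% |
| 56 | 63.7% to 86.3% | 62.3% to 84.5% | 61.6% to 85.6% |
| 30 | 59.5% to 90.5% | 57.3% to 87.0% | 55.9% to 88.9% |
| 28 | 59.0% to 91.0% | 56.6% to 87.3% | 55.1% to 89.3% |

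All rows use p = 0.75. At n = 30 that is 22.5 events, so the row is approximate; 21/28 is a whole count. From 56 to 30 raters the Wald half-width grows from 11.3 to 15.5 percentage points, a factor of √(56/30) = 1.37. Counting carers as well would give about 2 × 30 = 60 ratings, but these are pairs within dyads and not 60 independent observations.

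**The case against.** The strongest case on the other side has four parts.

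- **An interval is foreseen.** Sections 8.2 and 11.3 tie confidence intervals to estimating acceptability, 11.1 gives the summary measure, and 8.4 says that acceptability data feed the feasibility analysis with qualitative support. A reader might infer from 11.6.2 that the primary outcome gets no interval at all. The documents do not support that; what is missing is the line in the section where it belongs. This part stands.
- **A separate analysis plan is promised.** Interval method, and intervals for recruitment, retention and adherence, can properly wait for it. This stands for those details. It does not stand for the identity of the primary outcome: whoever writes the plan must contradict either 11.1 or 11.6.4.
- **The trial is descriptive.** The arms are not compared, no hypothesis is tested, and recruitment, follow-up, attrition and adherence are reported whatever their label. A reader might infer that the most favourable outcome will be chosen afterwards; nothing in the protocol shows such an intention. Section 11.6.4 may only mean that missingness and non-compliance are feasibility results in their own right and not nuisances to adjust for. That reading is plausible and lowers the severity, but the word primary is still wrong there.
- **The 75% and its interval might be the range meant in 11.3.** The sentence is unclear enough to allow this. An expected value with its sampling interval is not a continuation criterion, however, so the protocol should say what it means.

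The Cornell scale also appears under a primary outcomes heading in 8.4. It is not a further rival, because that list concerns measures proposed for the future trial.

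**Conclusion.** The protocol is wrong as written on one central matter and should be corrected, although the defect does not threaten the trial. It labels two different sets of outcomes primary, and its primary outcome analysis omits the one that justifies the sample size. The consequence is that no single result is fixed in advance as the answer to the feasibility question. There is no inflated error rate or bias to quantify.

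The measurable part is precision. If the denominator is the Behavioural Activation arm, the 95% interval at 75% runs from about 56% to 89% (exact) or 57% to 87% (Wilson), against 61.6% to 85.6% or 62.3% to 84.5% with 56 raters. This rests on two assumptions not in the protocol: 1:1 allocation, and that only treated participants can rate the intervention. The contradiction in labels depends on neither.

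**What to change.** 1. **11.1:** leave acceptability as the feasibility primary outcome.
2. **11.6.4:** remove the words that make missing data and non-compliance primary, and call them secondary, in line with 11.2.
3. **11.6.2:** add the proportion finding the intervention acceptable, with its 95% confidence interval. State the denominator, and state whether the rating by the person with dementia or by the carer is the primary one.
4. **11.3 (and the same text in 8.2):** if only Behavioural Activation participants rate acceptability, say that the denominator is about 30 under 1:1 allocation, not 56, and restate the expected interval with its method. If another denominator is meant, give it. In either case replace 59% to 87%, which none of the methods above gives at n = 56.
5. **11.3:** before the first randomisation, say what the acceptable ranges for continuation are. The form is for the trial team to choose.

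The cost is a few sentences of protocol amendment and one additional interval in the report. These changes do not themselves require a different sample size, data collection or trial conduct.
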